### ***6.11.2. Additional Analyses of the Primary Outcome***

Sensitivity analyses of the primary outcome measure will include a re-randomization test. The observed responses and randomization stratification covariates will be considered as a set of fixed values, and the treatment assignment then re-randomized using the same allocation mechanism from the trial. Approximately 5000 re-randomizations will be performed and the resulting p-values evaluated by:

- Comparing the observed difference in proportion of ORR with the re-randomized treatment differences
- Comparing the observed Fisher's test p-value for the comparison of treatments with the re-randomized treatment comparison.

### ***6.11.3. Secondary Efficacy Analyses***

#### **Response Endpoints**

The secondary efficacy endpoints of ORR and PR, PR and CR, and their exact 95% CIs will be estimated for each treatment arm and compared by 2-sided Chi-squared test or Fisher's exact test between 2 arms. A Fisher's exact test will be chosen over a Chi-squared test if in the 2x2 table, any of the expected cell counts are less than 5, or any cell has zero counts.

Efficacy data (CR, CRi, PR, and ORR) for patients receiving LY3039478 in combination with dexamethasone after failure of placebo in combination with dexamethasone will be tabulated, and further exploratory analyses of efficacy data conducted as warranted.

#### **Time to Event Endpoints**

For the secondary efficacy endpoints OS, RFS, and EFS, the Kaplan-Meier method (Kaplan and Meier 1958) will be used to estimate the survival curves as well as survival rates at various

prespecified time points (12 months for OS, 6 and 12 months for RFS and EFS) for each treatment arm.

The secondary efficacy endpoint DoR is subject to competing risk of death without relapse; therefore, the cumulative incidence of relapse (Gray 1988; Pepe and Mori 1993; Gooley et al. 2001) will be used. In the calculation, patients who did not have the event will be considered right-censored observations.

The comparison of the survival curves between treatment groups will be conducted by a log-rank test. Exploratory analyses for the comparison of the survival curves between treatment groups may additionally be conducted by a stratified log-rank test with some of the following stratification variables: initial diagnosis (T-ALL phenotype, T-LBL), response to last therapy (refractory or relapsed), age, number of prior therapies ( $\leq 2$ ,  $> 2$ ), NOTCH-1/FBXW7/RAS/PTEN status.

The Cox proportional hazard model (Cox 1972) with treatment as a factor will be used to estimate the hazard ratio and corresponding 95% CI with Wald's test p-value after adjusting for the following potential predictive/prognostic variables: initial diagnosis (T-ALL phenotype, T-LBL), response to last therapy (refractory or relapsed), age, number of prior therapies ( $\leq 2$ ,  $> 2$ ), NOTCH-1/FBXW7/RAS/PTEN status.

The unadjusted impact of patient baseline disease characteristics listed in Section 6.8 on OS and EFS will be explored using Cox proportional hazard models (Cox 1972) with the baseline characteristic as a factor (continuous variables split at median) and the hazard ratio and corresponding 95% CI plotted on a forest plot. Any characteristics found to be significant prognostic markers for EFS or OR may be included as additional covariates in COX proportional hazard model analyses to compare treatment arms.

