9.3. Method of Assignment to Treatment

9.3.1. Phase 1

Patients who enter the study during the Phase 1 portion will be assigned to receive LY3039478 and dexamethasone. Prior to enrollment into the study, an eligibility check must be conducted (for every patient) between the investigational site and the Lilly clinical research personnel, to confirm that the patient meets all enrollment criteria. Upon confirmation of eligibility, the sponsor will confirm the dose, cohort, and identification number assignment for each patient. No dose escalations (ie, to the next cohort) can occur without prior discussion and agreement with the responsible Lilly CRP.

9.3.2. Phase 2

Patients who enter the study during the Phase 2 portion will be randomized to receive either LY3039478 in combination with dexamethasone or placebo in combination with dexamethasone. Assignment to treatment groups will be determined by a computer-generated random sequence using an interactive web-response system (IWRS).

A dynamic allocation method, introduced by Pocock and Simon (1975) and extended for unequal treatment group sizes by Han et al. (2009), will be adopted to balance patient assignment between treatment arms, using a probability factor of 0.9, based on the following factors:

- age \leq 30 years versus $>$ 30 years
- T-ALL phenotype versus T-LBL, considered as 6 factors, representing the following 5 phenotypes of T-ALL:

TdT+, variable for all of the following: CD1a, CD2, CD3, CD4, CD5, CD7, CD8, CD34

- Pro-T-ALL: cCD3+, CD7+, CD1a-, CD2-, CD4-, CD8-, CD34+/-
- Pre-T-ALL: cCD3+, CD7+, CD1a-, CD2+, CD4-, CD8-, CD34+/-
- Cortical T-ALL: cCD3+, CD7+, CD1a+, CD2+, CD4+, CD8+, CD34-
- Medullary T-ALL: cCD3+, sCD3+, CD7+, CD1a-, CD2+, CD4+or CD8+, CD34-
- ETP T-ALL: Lack of CD1a and CD8 expression, weak CD5 expression with less than 75% positive blasts, and expression of 1 or more of the following myeloid or stem cell markers on at least 25% of lymphoblasts: CD117, CD34, HLA-DR, CD13, CD33, CD11b, and/or CD65
- response to last therapy: refractory/relapse within 1 year of last therapy vs. $>$ 1 year

The randomization parameter P will be set to 0.9 to maximize the benefit of the allocation procedure, whilst keeping treatment assignments unpredictable.

The IWRS will be used to assign bottles containing double-blind study drug to each patient. Site personnel will confirm that they have located the correct bottles by entering a confirmation number found on the bottles into the IWRS.

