12.2.13. Subgroup Analyses

Exploratory subgroup analyses of efficacy endpoints will be performed for stratification or potential prognostic variables (for example, NOTCH-1/FBXW7/RAS/PTEN status, age [≤ 30 , >30 years], initial diagnosis [T-ALL phenotype, T-LBL], ECOG status [0 or 1 vs 2], response to last therapy [refractory or relapsed], number of prior therapies [≤ 2 , >2]).

Other subgroup analyses may be performed as deemed appropriate.

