#### **5.3.2. Phase 2**

Patients who enter the study during the Phase 2 portion will be randomized to receive either LY3039478 in combination with dexamethasone or placebo in combination with dexamethasone. Assignment to treatment groups will be determined by a computer-generated random sequence using an interactive web-response system (IWRS).

A dynamic allocation method, introduced by Pocock and Simon (1975) and extended for unequal treatment group sizes by Han et al. (2009), will be adopted to balance patient assignment between treatment arms, using a probability factor of 0.9, based on the following factors:

- age  $\leq$ 30 years versus  $>$ 30 years
- T-ALL phenotype versus T-LBL, considered as 6 factors, representing the following 5 phenotypes of T-ALL:

TdT+, variable for all of the following: CD1a, CD2, CD3, CD4, CD5, CD7, CD8, CD34

- Pro-T-ALL: cCD3+, CD7+, CD1a-, CD2-, CD4-, CD8-, CD34+/-
- Pre-T-ALL: cCD3+, CD7+, CD1a-, CD2+, CD4-, CD8-, CD34+/-
- Cortical T-ALL: cCD3+, CD7+, CD1a+, CD2+, CD4+, CD8+, CD34-
- Medullary T-ALL: cCD3+, sCD3+, CD7+, CD1a-, CD2+, CD4+or CD8+, CD34-
- ETP T-ALL: Lack of CD1a and CD8 expression, weak CD5 expression with less than 75% positive blasts, and expression of 1 or more of the following myeloid or stem cell markers on at least 25% of lymphoblasts: CD117, CD34, HLA-DR, CD13, CD33, CD11b, and/or CD65

- response to last therapy: refractory/relapse within 1 year of last therapy vs. >1 year

The randomization parameter P will be set to 0.9 to maximize the benefit of the allocation procedure, whilst keeping treatment assignments unpredictable.

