## 6.8. Patient Characteristics

Patient demographics including age, sex, screening height, weight and body mass index, race, ethnicity, patient habits (caffeine/alcohol use) and country will be reported using descriptive statistics.

Baseline disease characteristics will be summarized by cohort (phase 1a, phase 1b) or randomized treatment arm (phase 2). Continuous variables will be summarized by median and range, and compared amongst treatment arms by ANOVA. Categorical variables will be summarized by frequency counts and compared amongst treatment arms by Fishers exact test. Statistical comparisons will be provided in phase 2 where data warrant only. The following disease characteristics will be summarized:

- Sex
- Age
- Diagnosis: T-ALL and T-LBL, with T-ALL additionally split by subtype:

TdT+, variable for all of the following: CD1a, CD2, CD3, CD4, CD5, CD7, CD8, CD34

- Pro-T-ALL: cCD3+, CD7+, CD1a-, CD2-, CD4-, CD8-, CD34+/-
- Pre-T-ALL: cCD3+, CD7+, CD1a-, CD2+, CD4-, CD8-, CD34+/-
- Cortical T-ALL: cCD3+, CD7+, CD1a+, CD2+, CD4+, CD8+, CD34-
- Medullary T-ALL: cCD3+, sCD3+, CD7+, CD1a-, CD2+, CD4+or CD8+, CD34-
- ETP T-ALL: Lack of CD1a and CD8 expression, weak CD5 expression with less than 75% positive blasts, and expression of 1 or more of the following myeloid or stem cell markers on at least 25% of lymphoblasts: CD117, CD34, HLA-DR, CD13, CD33, CD11b, and/or CD65
- ECOG status at randomization, or Lanksky status for Phase 1 Part B (pediatrics)
- Disease status: Refractory or relapsed, with relapse additionally split by: first relapse, second relapse, relapse after SCT
- Notch and/or FBWX7 mutational status: Yes, no [See Trinquand et al, 2013 for further details]
- RAS and/or PTEN abnormalities: Yes, no [See Trinquand et al, 2013 for further details]
- Extramedullary disease: Yes, no
- History of CNS leukemia: Yes, no
- Time since initial diagnosis
- Duration of first remission
- Response to last therapy: refractory, or relapsed with duration of remission <1 year, 1-2 years, 2-5 years, >5 years
- Number of prior courses of induction therapy (1, 2, 3, ≥4)
- Country

Other patient characteristics will be summarized as deemed appropriate.

Prior therapies and procedures e.g. stem cell transplant will be listed.

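### The planned Cox model codes response to last therapy as refractory v relapsed, not by the split that randomization balances, and no reason is given

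*SAP*

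**What the plan says.** **Allocation.** SAP 5.3.2 and protocol 9.3.2 minimise on three factors: age cut at 30 years, disease (five T-ALL phenotypes and T-LBL), and "response to last therapy: refractory/relapse within 1 year of last therapy vs. >1 year".

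**Analysis.** Under Time to Event Endpoints in SAP 6.11.3 (and likewise in protocol 12.2.8):
- Main comparison, with no strata: "The comparison of the survival curves between treatment groups will be conducted by a log-rank test".
- Stratified version, exploratory only: it "may additionally be conducted by a stratified log-rank test with some of the following stratification variables".
- Cox model, firmly planned: it "will be used to estimate the hazard ratio and corresponding 95% CI with Wald's test p-value after adjusting for" a list of variables.

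The list for the last two includes "response to last therapy (refractory or relapsed".

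**Elsewhere.** Protocol 12.2.13 uses the same two-way coding for subgroups: "response to last therapy [refractory or relapsed". SAP 6.8 has a third coding for the baseline table: "Response to last therapy: refractory, or relapsed with duration of remission <1 year, 1-2 years, 2-5 years, >5 years". One named factor thus has three codings, and neither document explains the differences.

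**The concern.** A factor is balanced at randomization because it is expected to predict outcome. Protocol 8.2 says as much and gives better power as one of the aims. That gain reaches the analysis when the model carries the factor as it was balanced. Here the model carries a factor of the same name cut at a different place.

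The point weighs most for the Cox model. It is planned rather than optional, and it is the only source of a treatment hazard ratio that SAP 6.11.3 describes. For ORR, SAP 6.11.2 has a re-randomization test that respects the actual allocation scheme. The time-to-event endpoints have no counterpart.

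**Working it through.** The plan states no figure on this point. Its power of about 82% belongs to Fisher's test on ORR, which uses no covariate, so it is not an input here.

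**Step 1. Set the two codings side by side** (SAP 5.3.2 against SAP 6.11.3).

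| Response to last therapy | Group at allocation | Group in Cox model and stratified log-rank |
|---|---|---|
| Refractory | refractory or early relapse | refractory |
| Relapse within 1 year | refractory or early relapse | relapsed |
| Relapse after 1 year | late relapse | relapsed |

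Only the middle row changes company. The two splits coincide only if that row is empty.

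**Step 2. How many patients are in the middle row?** Number = share of early relapses × 60. The documents give no share. As pure assumptions: 0% gives 0, 10% gives 0.10 × 60 = 6, and 30% gives 0.30 × 60 = 18. Inclusion criterion [2] points downwards. A patient in first or second relapse must have been refractory to at least one reinduction regimen. Where that regimen was the last therapy, the patient is refractory under both codings and does not move. Only a patient who later responded to a further regimen and then relapsed within a year can fall in the middle row.

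**Step 3. What could the recoding cost?** A small simulation illustrates it. From the documents: N = 60, allocated 2:1. Assumed:
- true treatment hazard ratio 0.5;
- exponential event times, with hazard lower for late relapses only;
- 2:1 balance within late and not-late groups;
- follow-up cut at three times the mean control event time of not-late patients;
- Cox model with treatment plus at most one covariate;
- 400 replicates in the first row, 350 in the others.

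Cells show power and mean estimated hazard ratio.

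| Refractory / early / late | Hazard ratio, late v rest | Randomized split | Refractory v relapsed | No covariate |
|---|---|---|---|---|
| 40 / 30 / 30% | 0.3 | 58%, 0.50 | 48%, 0.53 | 48%, 0.55 |
| 40 / 30 / 30% | 0.5 | 66%, 0.47 | 63%, 0.49 | 62%, 0.50 |
| 60 / 10 / 30% | 0.5 | 57%, 0.51 | 57%, 0.51 | 55%, 0.54 |

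With no treatment effect, in the first setting, the rejection rate was 4.5% with the randomized split and 4.3% with refractory v relapsed.

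Two cautions apply. The simulation error of a power near 50% is √(0.5 × 0.5 / 400) = 2.5 points, so differences of two or three points mean little. And the model makes late v not-late the true prognostic divide. If prognosis in fact divided at refractory v relapsed, the comparison would favour the SAP's coding. The table therefore sizes the cost only if the balancing factor was well chosen.

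**Step 4. Could the stratified log-rank simply take all the allocation levels?** Age 2 × disease 6 × response 2 = 24 cells. 60 / 24 = 2.5 patients per cell, or about 1.7 v 0.8 at 2:1. Many cells would hold one arm only and contribute nothing to the test.

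**The case against.** The case for leaving the text alone is a fair one.
- The Cox covariates are offered as potentially prognostic variables, not as a copy of the allocation factors. Refractory v relapsed is a defensible prognostic split.
- The stratified log-rank is exploratory, optional, and free to use only some of the listed variables.
- SAP 6.8 records remission duration in bands, from which the randomized split could largely be rebuilt. SAP 6.11.3 lets baseline characteristics found prognostic enter the Cox model.
- Inclusion criterion [2] may leave few patients who change group.

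Most of this stands and keeps the point small. It does not remove it. Adjusting for refractory v relapsed in addition would be unobjectionable; the weakness is that it replaces the balanced factor without a reason. The route through SAP 6.8 is optional, depends on what turns out significant, and measures remission duration rather than time from last therapy.

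A reader might infer that the analysis drops the allocation factors generally. The documents do not support that. Disease is carried over in the list, and age is listed too. Its 30-year cut is not repeated there, but protocol 12.2.13 gives it for subgroups, and a Cox model may use age as a continuous variable. Only a log-rank stratum would need the cut stated.

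**Conclusion.** The mismatch is real and stands in the current text of both documents. It concerns one of three balancing factors, in one planned secondary model and one optional exploratory test. The possible cost is lost precision and some attenuation of the adjusted hazard ratio. In the illustration this ran from nothing, with 10% early relapses, to 10 points of power (58% v 48%) with 30% early relapses and a strong prognostic effect. Those shares and effects are assumptions.

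Three stronger readings are tempting but not supported:
- *The recoding loses the balance that minimisation built.* Balance is a property of the allocation, and a covariate's coding does not undo it.
- *The test becomes invalid.* The illustration shows no inflation of type I error (4.3%, against 4.5% with the randomized split). The primary Fisher test on ORR and the main log-rank test carry no covariate and are untouched.
- *A large part of the trial changes stratum.* No share is given, and the eligibility rule suggests that the number may be small.

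This is a minor point: a free improvement rather than a flaw in the main inference.

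**What to change.** In SAP 6.11.3 and protocol 12.2.8:
- In the Cox model, enter response to last therapy at the level recorded in the IWRS (refractory or relapse within 1 year, against more than 1 year). Do the same in the stratified log-rank if this factor is among those chosen.
- Keep refractory v relapsed as a subgroup factor or an additional covariate. If it is preferred as the main coding, state why.
- If age is used as a log-rank stratum, use the randomized cut (at most 30 v over 30 years). It may stay continuous in the Cox model.
- Do not cross all allocation levels as log-rank strata; 24 cells for 60 patients is too sparse. Name beforehand the few that will be used.

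Cost: a few lines of text and no new data, since the IWRS must hold these levels to run the allocation. Protocol 12.2.1 lets minor changes of method be described in the SAP before the aggregate database is unblinded, so the SAP can be changed first and protocol 12.2.8 brought into line with it.

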After the last patient on Part A has completed Cycle 1 and the recommended dose for the Phase 2 portion is determined, the randomized, Phase 2 portion will begin following an interim review of the data. The patient population in the Phase 2 portion of the study will be identical to the patient population assessed in Part A.

In the Phase 2 portion, 60 patients will be randomized in a 2:1 ratio to receive either LY3039478 in combination with dexamethasone administered 24 mg orally on Days 1 to 5 every other week or placebo in combination with dexamethasone administered 24 mg orally on Days 1 to 5 every other week. Placebo or LY3039478 will be administered orally TIW at the recommended dose from Part A. Patients will receive treatment until progression or meeting discontinuation criteria as outlined in the protocol.

[figure not shown]
Patients discontinuing the study for treatment failure will be unblinded after discontinuation. A crossover to LY3039478 in combination with dexamethasone will be allowed for patients who were receiving placebo in combination with dexamethasone.

A futility interim analysis will be performed in the Phase 2 portion of the study when 30 patients have completed the CR status determination. The analysis will assess the safety profile, verify that the chosen regimen is clinically feasible, and determine if the futility criteria have been met.

An internal assessment committee consisting of (at minimum) a Lilly Medical Director, a Lilly CRP not associated with the study, a PK scientist, and a statistician will examine the interim results and make recommendations about the trial.

The total sample size for this study is estimated to be approximately 86 to 92 patients.

There is no fixed duration of treatment; patients will remain on study until they fulfill 1 of the criteria for study discontinuation.

 Phase 2 patients who discontinue the study due to relapse/refractory disease or treatment failure may crossover to treatment with LY3039478 + Dexamethasone.

Abbreviation: MTD = maximum tolerated dose.

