**Figure JJCB.5.1. Illustration of study design.**

## 5.2. Determination of Sample Size

Approximately 86 to 92 patients will be enrolled in this multicenter study.

In the Phase 1 portion of the study, the primary objective is to determine the MTD and the recommended dose for Phase 2. Approximately 13 to 16 patients will be enrolled into the adult (Part A), and approximately 13 to 16 patients will be enrolled in the pediatric (Part B) cohorts sequentially and without randomization to dose. The total sample size per cohort will be determined by DLTs.

In the Phase 2 portion of the study, the primary objective of this study is to compare the ORR (CR plus CRi) rate between LY3039478 administered with dexamethasone and placebo administered with dexamethasone, in adult patients with relapsed/refractory T-ALL/T-LBL. Approximately 60 evaluable patients will be randomized to the 2 treatment arms in a 2:1 ratio (40 randomized to LY3039478 and dexamethasone and 20 randomized to placebo and dexamethasone).

Assuming the ORR for the LY3039478 and dexamethasone arm is 40% and the ORR of the placebo and dexamethasone is 5%, the sample size of 60 evaluable patients will give approximately 82% statistical power to detect the difference, using a 2-sided Fisher's test at the significance level of 0.05, with 1 futility interim once the 30th enrolled patient completes the remission status determination.

Patients who are randomized and do not achieve a CR or CRi will be considered as nonresponders in the primary analysis for ORR.

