## 6. A Priori Statistical Methods

### 6.1. General Considerations

Phase 1 Part A, Phase 1 Part B and Phase 2 study parts will be reported in separate TFLs.

Results of descriptive analyses and estimates from inferential analyses will be presented by dose level cohort (phase 1) or by treatment (phase 2). In the phase 2 study part, an additional group will be included in primary efficacy and safety TFLs to represent data for patients receiving LY3039478 in combination with dexamethasone after failure of placebo in combination with dexamethasone.

All tests of treatment effects will be conducted at a 2-sided alpha level of 0.05, unless otherwise stated. All tests of interactions will be conducted at a 2-sided alpha level of 0.1, and all CIs will be given at a 2-sided 95% level, unless otherwise stated.

The assumptions for each statistical method will be evaluated. If there is violation of assumptions, alternative statistical methods may be used.

Additional exploratory analyses of the data will be conducted as deemed appropriate.

For continuous variables, summary statistics will include number of patients, mean, median, standard deviation, minimum, and maximum. Categorical endpoints will be summarized using number of patients, frequency, and percentages. Any missing longitudinal data will not be imputed, rather estimated from an appropriate random mixed effects model. Transformations will be applied where assumptions behind any analysis are better satisfied by data being transformed onto an alternative scale. All results from any of these analyses will be back transformed to the original scale. Alternatively, nonparametric methods will be applied.

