One futility interim analysis is planned in Phase 2 once 30 patients are randomized and have completed the CR status determination. PK and/or PD data, if available, will also be reviewed at this interim analysis. Given the small sample size per treatment arm at the interim analysis: n=10 for the placebo plus dexamethasone (control) arm, and n=20 for the LY3039478 plus dexamethasone (test) arm, and the low anticipated ORR for the control arm ( $\leq 5\%$ ) in this study, no formal inferential analysis is planned at the interim analysis. The AC may recommend to stop the study for futility if the observed improvement in response rates is less than 5%. For example, if the control arm has 1 response in 10 patients (10%), the test arm would need to observe at least 3 responses in 20 patients (15%) to warrant continuing the study. This decision criterion is

provided to the AC for guidance only. Any recommendation to stop for futility will be based on AC review of all available safety and efficacy data in addition to ORR rate.

Simulations have been conducted in order to understand the operating characteristics of the futility rule and the impact on statistical power is considered minimal. It is not planned to stop the trial early for efficacy, thus there are no adjustments for multiplicity.

Only the assessment committee is authorized to evaluate unblinded interim efficacy and safety analyses. Study sites will receive information about interim results ONLY if they need to know for the safety of their patients.

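### The adjusted Cox model, the only planned source of a treatment hazard ratio, has too many parameters for 60 patients (11 on the SAP's own codings), so its 95% CI is too narrow; for RFS it may not be estimable

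*SAP*

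**What the plan says.** Under Time to Event Endpoints, SAP 6.11.3 compares the survival curves by an unadjusted log-rank test. It then takes the hazard ratio, 95% CI and Wald p-value from a Cox model with treatment as a factor, "after adjusting for the following potential predictive/prognostic variables". The list is initial diagnosis (T-ALL phenotype, T-LBL), "response to last therapy (refractory or relapsed), age, number of prior therapies" (cut at 2), and NOTCH-1/FBXW7/RAS/PTEN status. Protocol 12.2.8 has the same model. Neither text gives degrees of freedom, an event count or a cap on covariates, and neither exempts RFS.

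The SAP next plans one-at-a-time Cox models of the SAP 6.8 baseline characteristics on OS and EFS, shown as a forest plot, and adds: "Any characteristics found to be significant prognostic markers for EFS or OR may be included as additional covariates" when the arms are compared. 'OR' is probably a slip for OS, since the preceding sentence names OS and EFS. Those one-at-a-time models estimate the effect of each characteristic, not of treatment.

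SAP 5.1 sets the size: "60 patients will be randomized in a 2:1 ratio". SAP 6.1 sets the level: "All tests of treatment effects will be conducted at a 2-sided alpha level of 0.05". SAP 6.5 plans no multiplicity adjustment.

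**The concern.** The standard error and Wald test of a Cox model rely on having many events per parameter. With few, the model-based standard error is too small, the 95% CI is too short and the test rejects too often. Here five covariates are forced into the only treatment hazard ratio the plan produces, and that ratio is what a reader will take as the size of effect on OS and EFS. RFS is confined to responders, so the same model meets far fewer patients there. The option to add covariates after seeing which are significant also means that the model behind the reported ratio is not known in advance.

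**Working it through.** **The plan's own figure.** The documents give no power, event count or parameter count for the Cox model. The only operating figure is for ORR: 60 patients "will give approximately 82% statistical power to detect the difference" (40% v 5%, two-sided Fisher). Exact enumeration gives 87.8% without the interim and 87.7% with the futility look treated as binding. The stated 82% is therefore not reproduced and is conservative, but it has no bearing on this point.

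**Parameter count.** Inputs: treatment 1; response to last therapy 1, age 1 and prior therapies 1 (SAP 6.11.3); diagnosis 5, from six levels (SAP 5.3.2 and 6.8); mutation status 2, from two yes/no variables (SAP 6.8).

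- SAP codings: 1 + 5 + 1 + 1 + 1 + 2 = 11.
- Leanest reading (T-ALL v T-LBL, one mutation variable): 1 + 1 + 1 + 1 + 1 + 1 = 6.
- Richest reading (four separate genes): 1 + 5 + 1 + 1 + 1 + 4 = 13.

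**Behaviour at HR 1.** Simulation of 60 patients, 2:1, Wald test at 5%, 4,000 trials per row, prognostic covariates. Event counts, prevalences and covariate effects are assumptions because the documents give none. The Monte Carlo standard error of a rejection rate near 8.5% is √(0.085 × 0.915 / 4000) = 0.4 points.

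| Events | Events per parameter (events / 11) | 11 parameters: rejects / CI covers | Plus covariates found significant: rejects / CI covers | Treatment only: rejects | Log-rank: rejects |
|---|---|---|---|---|---|
| 57 | 5.2 | 8.5% / 91.5% | 8.8% / 91.1% | 5.0% | 5.4% |
| 48 | 4.4 | 9.4% / 90.6% | 9.5% / 90.5% | 5.8% | 6.1% |
| 36 | 3.3 | 8.8% / 91.2% | 9.1% / 90.9% | 4.8% | 5.4% |
| 24 | 2.2 | 8.4% / 91.6% | 9.4% / 90.6% | 4.7% | 5.7% |

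- With covariates that have no effect, the 11-parameter model rejects 8.1% at both 36 and 24 events, with 91.9% coverage. Under approximate minimised allocation it rejects 8.1 to 8.6%, and the log-rank test 3.4 to 4.8%. A separate simulation gave 8.6% rejection and 91.4% coverage at 51 events, and 7.6% and 92.4% at 36.
- The cause is an understated standard error. At 36 events with null covariates the mean model SE is 0.416 against an empirical SD of 0.483 (1 − 0.416/0.483 = 14% too small). At 24 events with prognostic covariates it is 0.529 against 0.645 (18% too small).
- Six parameters: 6.9% at 57 events and 5.9% at 36. Other runs gave 5.3 to 7.2%.
- Treatment plus three binary factors (4 parameters): 4.8 to 6.4% over three separate simulations at 51 or 36 events.

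**Effect of selection.** Adding covariates found significant raises rejection by 0.3, 0.1, 0.3 and 1.0 points in the four rows. Selection without the forced covariates rejects 5.1 to 5.2%. The candidates were simulated with one degree of freedom each; multi-level ones would add more parameters.

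**At true HR 0.50.** With 57 events the 11-parameter model has median estimate 0.466 and coverage 91.0%. In a separate run with 51 events it rejected 62.2% against 62.4% for the 4-parameter model, with coverage 89.5% against 92.2%. The extra covariates bought no power there.

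**RFS.** SAP 6.11 defines RFS for CR/CRi patients only. At the planned rates that is 40 × 0.40 + 20 × 0.05 = 16 + 1 = 17 patients. The chance of no control responder is 0.95^20 = 36%. In simulated sets of 17 responders, the 11-parameter model was non-estimable or degenerate in 48%.

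**The case against.** The count of 11 is an inference. The Cox text does not say that phenotype enters as six levels; that coding comes from the allocation factors and the baseline table. On the leanest reading the excess is small. This stands, and it is why the range has to be given; it is also a reason to write the coding down.

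A reader might infer that inference on OS and EFS as a whole is unsound. The documents do not support that. The planned test of the curves is the unadjusted log-rank test, which stays near 5%. The primary ORR comparison is a Fisher test that does not use this model, and no multiplicity-controlled claim rests on the Cox p-value.

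A reader might also infer that picking covariates by significance is a main cause of the inflation. It is not: it adds at most about 1 point, it is optional in the SAP, and it selects on association with outcome rather than on the treatment effect. The objection to it is that the reported hazard ratio then depends on the data. Nor would likelihood-ratio p-values cure the problem. At 11 parameters they rejected 9.6% against 9.4% for Wald (51 events) and 8.9% against 8.4% (36 events).

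SAP 6.1 allows alternative methods if assumptions fail. That generic clause sets no limit on this model and does not correct a stated specification. Finally, dropping mutation status removes a variable tied to a secondary objective. That is a real though small cost, taken up in the fix.

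**Conclusion.** The point holds in a limited form. On the SAP's own codings the nominal 95% CI for the treatment hazard ratio covers about 91 to 92%, and the 5% Wald test rejects about 8 to 9% at HR 1. On the leanest coding rejection is about 5 to 7%. Nearly all of the excess comes from the number of forced parameters relative to events. These sizes rest on assumed event counts (24 to 57), prevalences and prognostic effects; the direction was the same in every setting tried. For RFS the trouble is estimability: about 17 patients, 16 v 1, cannot support the model. This is a secondary-analysis defect that should be corrected before unblinding. It does not threaten the primary conclusion.

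**What to change.** In SAP 6.11.3:

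1. Limit the adjusted Cox model for OS and EFS to treatment plus the three allocation factors: age, response to last therapy, and diagnosis collapsed to T-ALL v T-LBL. That is 4 parameters.
2. State each coding. Allocation (SAP 5.3.2) splits response to last therapy at 1 year, while the Cox text uses refractory or relapsed; choose one and say so.
3. Report the unadjusted hazard ratio and 95% CI alongside.
4. Delete the sentence allowing significant characteristics to be added. Keep the forest plot as description, and correct 'OR' there if OS is meant.
5. State that the adjusted model will not be fitted to RFS.

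The cost is wording. Protocol 12.2.8 carries the same covariate list, but protocol 12.2.1 allows minor modifications of analysis methods to be described and justified in the SAP before the aggregate database is unblinded. The small downside is that mutation status and number of prior therapies are then examined only in the planned subgroup and biomarker analyses (SAP 6.13.1 and 6.15, protocol 12.2.13). The 4-parameter model is not exactly nominal either (4.8 to 6.4%), so its p-value should be read as supportive of the log-rank test.
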